None- the event can be readily explained by the participant's underlying medical condition or concomitant therapy, and no relationship exists between the study drug and the event. In this event, an alternative etiology must be indicated.

Unlikely-the temporal relationship between the event and the administration of the study drug is uncertain and the event can be probably explained by the participant's medical condition or other therapies.

Possible- there is some temporal relationship between the event and the administration of the study drug and the event cannot be explained by the participant's medical condition or other therapies.

Probable- the temporal relationship is compelling between the administration of the study drug and the event cannot be explained by the participant's medical condition or other therapies.

Severity

Adverse events should be graded for severity and noted in the description of the event. A severity category of mild, moderate or severe, as defined below, should be determined and entered on the appropriated AEF.

Mild- causing no limitation of usual activities.

Moderate- causing some limitation of usual activities.

Severe- causing inability to carry out usual activities

Definition of Serious Adverse Event (SAE)

An SAE is any AE, occurring at any dose and regardless of causality that:

- Results in death
- Is life-threatening; the subject is at immediate risk of death from the reaction as it occurs.
- Is significantly or permanently disabling or incapacitating;
- Requires or prolongs inpatient hospitalization;
- Results in permanent disability; results in a congenital anomaly;

Significant medical events that may not result in death, be immediately life threatening, or require hospitalization may be considered to be SAEs when, based on the medical judgment, they may jeopardize the participant and may require intervention to prevent one of the outcomes defined above as SAE.

Reporting of Serious or Unexpected Adverse Events

In the event of any “**serious**” and/or “**unexpected**” adverse drug experiences during this study, the Principal Investigator will notify the following:

[name], Department of Quality Management New York State Psychiatric Institute [name]

In addition to the report to quality management, relevant data on the event and any available follow-up reports will be reported to NIDA's Project Officer [name] via email and also via using the Serious Adverse Event Tracking and Reporting System (SAETRS) within 72 hours of the event occurrence. The initial notification will indicate that the event occurred and the IRB/DSMB was notified. The PI will follow-up with the PO as the evaluation of the SAE proceeds, on whether the SAE was related or not to the trial. These follow-ups will occur as the evaluation moves forward, and not wait until the final conclusions are determined.

The Investigator will also provide written notification of the SAE to the IRB. The Incident Review Committee will also review the SAE and suggest appropriate actions and, if necessary, study modifications.

The DSMB and study PI will determine whether the seriousness of the event warrants removal of any participant from the study. Appropriate diagnostic and therapeutic measures will be instituted and the participant will be kept under observation for as long as is medically indicated. IRB actions following the

occurrence of an SAE will be reported to NIDA. Any conflict of interest in the data and safety monitoring will be disclosed. The SAEs and AEs will be reviewed by the DSMB on a regular basis.

F3. Management of SAEs and other study risks

Procedures for Minimizing Risks:

1) Screening Procedures

In order to minimize the risk associated with the study, subjects undergo a comprehensive medical and psychiatric evaluation during the screening procedure. The baseline medical evaluation consists of a physical examination, blood chemistry profile (including liver function tests), complete blood count, urinalysis, serum pregnancy test, urine toxicology and is designed, along with the clinical history, to detect chronic and/or unstable medical illnesses. A comprehensive psychiatric assessment is performed during the screening process, and is intended to detect and assess all past and current psychiatric disorders. The eligibility criteria (see above) are designed to minimize the medical and psychiatric risks to participants by excluding those for whom participation would place them at an increased risk. Special attention will be given to patient's concurrent use of medications. Participants on medications that meet exclusion criteria will not be included in the study. If participants have recently completed another study at STARS, we will ensure, as with other medications, that there are no drug-drug interactions with the possible recent exposure to other study medications or will ensure proper time for wash-out between studies.

2) Study Procedures

Participants will be informed about the possible side effects and risks (listed above) of taking buprenorphine and extended-release naltrexone both alone and in combination with other medications through extensive discussions with staff psychiatrist during the consent process. Participants will be told to contact the clinic if they experience any adverse effects and given the number for the 24-hr physician on-call. Participants' mental status and physical health are monitored weekly during the study period by a psychiatrist. Vital signs will be obtained at each study visit. At clinic visits, a physician will assess participants for signs and symptoms of adverse effects of study medications, noting which if any symptoms are present, the severity of the symptoms, make adjustments to study medication dose, discontinue study medication, or withdraw the participant from the study if needed.

Female participants who are engaging in sexual activity with men must use adequate methods of contraception which will be discussed repeatedly during the screening process. Serum pregnancy tests will be conducted during screening and urine pregnancy tests will be performed monthly during the study. If a female participant does become pregnant or wishes to become pregnant, study medication will be immediately discontinued, she will be withdrawn from the study, and offered continuing non-pharmacological treatment (psychotherapy).

3) Procedures to Minimize Other Risks:

With regards to the risks of blood draws, only staff trained in phlebotomy will draw blood from participants to minimize risks of infection. Participants will be warned of the possible associated discomfort and slight bruising following blood draws. They can decline blood draws at any time.

We aim to reduce the risk of using cash card reimbursements and incentives to buy drugs by keeping reimbursements at a low monetary value. The monetary incentives for completion of study related activities are felt to be modest, appropriate, and limited and also in card form. This payment schedule has been used successfully in treatment studies in our clinic and others with no observed effect of increased drug use.

With regards to risks associated with interviews, rating scales, and questionnaires, patients are informed that they may refuse to answer any questions and may ask to stop at any time. If participants become upset during the interviews/assessments, assistance will be made available to them.

4) Relapse during outpatient naltrexone induction

During the detoxification phase of the study, particularly during washout day and during first few days when naltrexone is introduced if a patient resumes regular opiate, including buprenorphine, use then taking naltrexone, particularly naltrexone injection, may precipitate opiate withdrawal, which may be severe. Patients will be warned not to take the naltrexone if they resumed any level of opiate use, and opiate abstinence will be confirmed by urine toxicology prior to administering the next daily dose of naltrexone.

5) Procedures for Missed Doses of Long-acting Naltrexone: Missing a scheduled Vivitrol injection is the most important threat to the success of long-acting naltrexone maintenance. In the event of a patient missing a scheduled injection, the clinic staff will immediately attempt to contact the patient to re-establish commitment to the naltrexone treatment and reschedule the injection within a 48-hour period, or as soon as possible thereafter, based on clinical judgement (i.e., after a clinical assessment and naloxone challenge if indicated). If the patient cannot attend the treatment clinic within that time-frame, or cannot be located, the treatment team will use previously obtained locator information in an effort to locate the patient through emergency contacts and get him/her in for a clinic visit. If opioid use occurs in combination with a missed Vivitrol injection, a naloxone challenge will be administered to confirm that the next long-acting naltrexone injection will be safely tolerated.

6) Relapse during post-medication follow-up phase

It is possible that some patients may have difficulty remaining abstinent after XR-NTX or buprenorphine are discontinued. All participants will be monitored closely during the follow-up period for signs of destabilization such as increase in cravings, or opioid use initiation. Participants who are unable to maintain abstinence off opioids will be offered resumption of maintenance treatment with buprenorphine, and once stable will be transferred to a provider in the community.

Psychiatric Monitoring and Removal from Study

Participants' mental and physical status is monitored weekly by the physician. The psychiatrist will assess appropriateness for continuation in the research study on a continuous basis, and will remove from the trial patients with significant clinical deterioration or noncompliance of a type that could be dangerous. Although unlikely, it is possible that patients may become psychotic or depressed, requiring discontinuation of study medication, and possibly psychiatric intervention. The weekly monitoring of patients, along with ongoing evaluations with structured assessments, such as the Hamilton Depression Scale, should allow us to detect these psychiatric disturbances early and intervene appropriately.

Although a patient might potentially attempt to overdose with buprenorphine, individuals who are at significant risk for suicidality will be excluded. Further, buprenorphine is a partial agonist and has a ceiling effect on respiratory depression; overdoses involving sublingual buprenorphine are rare and typically involve taking of toxic amounts of alcohol or benzodiazepines in combination with buprenorphine. Patients will be provided with a 1--2 weeks supply of buprenorphine throughout the study at a time.

Patient Education

All patients will be informed through the consent process and consent form and discussions with the research psychiatrist of the possible side effects and risks enumerated above. In addition, at weekly visits the research nurse or psychiatrist will query about side effects and treatment emergent symptoms. Patients will be warned that risks, as yet unknown, may occur when combining study medication with opioids or with other street drugs or alcohol. Patients will give informed consent before entering the study. Patients are instructed to call us if any untoward effects occur and are given the phone number of our 24—hour answering service. One of the study-- affiliated physicians is on call 24 hours per day to answer questions and handle clinical emergencies.

Opioid Overdose Responder Training

The Substance Abuse Treatment and Research Service (STARS) is a registered opioid overdose prevention program through the New York State Department of Health since June 2015. Our program is in compliance with 10 NYCRR 80.138 that permit non-patient specific prescriptions for naloxone, as well as shared access to and use of naloxone by appropriately trained individuals. As part of this program we offer free intranasal naloxone and training for overdose responders to any patient who self-identifies as an opioid user.

Significant Other Contact

Upon entry to the study, the participant is informed that, if s/he agrees, the staff would prefer to have the contact information of someone who knows them well, to periodically assess how they are doing or to aid in case of emergency. Providing this information is not contingent on participating in the study. The participant, if he or she agrees, will then inform the individual that they may be contacted by the study staff. Only after the participant has informed the individual about the possible contact by the staff will the contact information be provided and the consent form addendum be signed.

Study Discontinuation

Criteria for removal from the study will include:

(1) substantial alcohol and other drug use that endangers the patient or requires a higher level of care such as inpatient or residential treatment; (2) psychiatric or medical deterioration that cannot be managed safely in the context outpatient treatment offered at the study clinics (e.g., acute suicide risk, acute medical problems); (3) Ongoing non-adherence with recommended clinical visits, absence from the clinic for more than 21 days; and (4) Pregnancy.

Patients who are exited from the trial for any reason will be offered a continued treatment in the community unless a higher level of care is indicated (inpatient or residential treatment), or the patient requests treatment elsewhere, in which care help with arranging referrals will be offered. Participants will be offer a weekly supply of buprenorphine for up to 30 days if they are being transitioned to another treatment program if they are removed from the trial. A clinic staff member, with physician backup, is available 24 hours per day by phone in case of emergency.

Participants may be removed from the trial if they repeatedly miss scheduled appointments or clinical worsening necessitates more intensive treatment (drop out criteria are defined above). Subjects who develop serious psychiatric symptomatology (e.g., psychosis, suicidal ideation, severe depressive symptoms) during the study period will be dropped from the study and appropriate clinical referrals will be made. A patient who's continued opioid use, places them at risk for self-destructive behavior or otherwise places them at significant risk will be discontinued from the study. This would include, but not be limited to, patients who become unconscious after using, engage in destructive or violent behavior while intoxicated, report driving while intoxicated, or develop medical complications from their opioid use. In all cases where subjects are discontinued from the study, the clinical research staff will assume clinical responsibility for the subjects until clinical referrals are operational.

In case that the patient is removed from the research trial for medical reasons, or is requesting withdrawal from the study, he/she will be retained in open treatment for the remaining study period. Upon removal of a patient from the trial due to clinical deterioration, the patient will be referred for appropriate follow-up treatment, in most instances either intensive outpatient or residential treatment. The PI or a study psychiatrist is available 24 hours/day by phone and/or beeper in case of emergency.

If a patient is discontinued from the study, or decides to withdraw, or relapses during study the participation, the patient will get treated with buprenorphine until they are linked with a referral for continuing buprenorphine treatment. Participants will receive a one-week supply of buprenorphine at a time during the transition process.

Management of SAE's

Serious adverse events (SAEs), as defined by the FDA, will be systematically evaluated at each clinic visit. Any SAE, whether or not related to study medication, will be reported to the IRB and NIDA. The initial SAE report will be followed by submission of a completed SAE report to both institutions.

In the event that a patient either withdraws from the study or the investigator decides to discontinue a patient due to SAE, the patient will have appropriate follow-up medical monitoring. Monitoring will continue until the problem requiring hospitalization has resolved or stabilized with no further change expected, is clearly unrelated to study medication, or results in death. Outcome of SAEs will be reported to NIDA as soon as this information becomes available. A summary of the SAEs that occurred during the previous year will be included in the annual progress report to NIDA.

G. TRIAL EFFICACY

Interim analyses are not planned for this study.

H. DATA AND SAFETY MONITORING PLAN ADMINISTRATION

H1. Responsibility for data and safety monitoring

The study Principal Investigator, [name], is primarily responsible for the data and safety monitoring. He will be assisted by [name], study Medical Monitor, and other STARS staff physicians.

H2. Frequency of DSM

Ongoing data and safety monitoring will be conducted weekly during research meetings. Every three months, the PI and the medical monitor will review the number of patients enrolled, the number who completed the protocol, the number who dropped out of the protocol prior to completion (and reason why), any adverse events, procedures for assuring patient privacy and confidentiality, and the quality and integrity of the data collected. Corrective action will be taken if needed. IRB protocols and informed consent documents will be reviewed annually by the IRB. Reports of enrollment and retention and reporting of adverse events are required with these renewals. In addition, all studies involving human subjects are periodically and systematically reviewed by the New York State Quality Assurance Staff. These procedures assure protocol compliance by conducting unannounced reviews of participants' research charts, comparing research charts to the IRB protocol. All serious adverse events will be reported to the DSMB in a timely fashion. This report will also be forwarded to the NIDA's Project Staff [name] (PO) upon receipt.

In addition, a separate Data Safety and Monitoring Board (DSMB; see below for details) will meet yearly.

H3. Content of DSM report

Annually, the DSMB will prepare and submit a report to NIDA. This report will include the following:

1. Brief description of the trial
2. Baseline socio-demographic characteristics
3. Retention and disposition of study participants
4. Q.A. Issues
5. Regulatory Issues
6. AEs
7. SAEs
8. Efficacy

I. DSM BOARD PLAN

The proposed study will have a Data Safety and Monitoring Board (DSMB), that will be chaired by [name], a Division Chief, and will include [name], a senior investigator in the Division, and [name] who is a Director of the research clinic. In addition, [name], an experienced investigator based in the University of Virginia School of Medicine, who published research involving buprenorphine maintenance, will join the DSMB. The DSMB will meet before the study launch and annually afterwards to conduct initial and ongoing study review and review all Adverse Events that occurred in the study. The DSMB will meet within a week of the occurrence of any Serious Adverse Event (SAE). For each SAE, the Principal Investigator and covering physician will present a synopsis of how it occurred and how the incident was handled clinically. In this way the team can assess how the event was managed and if there are any recommendations that will maintain the high quality of the care that we provide to our research participants. All DSMB members will be asked to submit in writing any potential conflict of interest pertaining to the study. DSMB will prepare a report to NIDA in response to any SAE review meetings, and will submit a DSM report annually (as outlined above in section H3).

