Urine samples will be collected at every visit, and we will use onsite testing to provide immediate feedback on opiate use to the participant and the treatment team. Blood chemistry will be obtained at baseline and end of study (week 25). Urine Pregnancy tests will be obtained at baseline, at once monthly (or prior to administration of XR-NTX).

We will collect 4ml of saliva, 50ml of urine, and 4, 6-7ml blood from subjects at Baseline, after randomization (3 weeks after 1st injection of XR-NTX, or 1 week after completing bup taper), during post randomization month 2 (1 week after 2nd XR-NTX injection, or 4 weeks after completion of bup taper), and at end of study to be examined for biomarkers. From these we will isolate extracellular vesicle-containing pellets and evaluate their contents using advanced -OMICs analyses, in order to identify molecular signatures that differ across subjects before and after ending treatment with buprenorphine.

Assessment Instruments

Create a table or give a brief description of the instruments that will be used for assessment

Physiological Measures

Medical History and Physical Exam: A comprehensive medical history and physical examination will be performed during the screening process. All potential participants will be offered the opportunity to be referred to receive free HIV risk reduction education, as well as HIV testing and counseling.

Pregnancy Testing: Serum pregnancy testing will be performed on all females during screening and urine pregnancy tests will be performed at baseline and monthly afterwards.

Serum laboratory examination: Complete blood count, electrolyte, and liver function tests will be performed during the screening process and at the end of study.

Urinalysis: Laboratory urinalysis (glucose, protein, ketones, pH, specific gravity, and microscopic analysis) will be performed during the screening process and at the end of study.

Urine Toxicology: Urine samples will be collected under directly--observed conditions during screening and at each study visit. To provide immediate feedback to the participant, the Abuscreen On--Trak system (Roche Diagnostics) will be used to identify opiates (morphine, oxycodone, buprenorphine, methadone). In addition, the sample will be analyzed for substances of abuse, including THC, alcohol, opioids, cocaine, benzodiazepines, amphetamines, and barbiturates.

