Contingency Management and Subject Compensation: Subjects will be encouraged to come for the clinical evaluations and for CBT sessions as described in this protocol. To minimize missed sessions, they will be reimbursed for transportation expenses, for providing data, and for time spent in completing study assessments in accordance with local site's IRB policies. Contingency management procedures which have been shown to successfully improve many behaviors ranging from medication compliance to adherence to protocol activities will be applied to this study. Subjects will earn chances at each visit to draw vouchers from a prize-bowl. A subject must complete all visit requirements to be able to draw vouchers at the end of a visit. If study medication is discontinued due to adverse events, subject will continue to draw vouchers based on the schedule below as long as they continue all other visit requirements are completed. Participants will earn one draw for each consecutive visit made, with a bonus 3 draws for every 3 consecutive weeks. If a participant misses a visit, their draws are reset. Each draw has a probabilistic chance of yielding one of four outcomes; an encouraging statement (e.g. 'good job'), a small prize valued at \$2.50, a large prize valued at \$20, or a jumbo prize valued at \$100. The probability of each particular outcome is fixed for every draw and is based on the relative number of slips for each prize category in the prize bowl. Using Petry et al.s (2005) framework each prize bowl will have 500 prize slips. 250 slips will be an encouraging statement (50% of the total slips), 209 will be for small prizes (41.8%), 40 slips will be for large prizes (8%), and 10 slips will be the jumbo prize (0.2%). Patients will earn 1 additional draw for every consecutive week of abstinence (all urine samples for a treatment week test negative). The increasing number of earned draws during the protocol follows the escalating incentive structure employed in other CM based treatments (Higgins et al., 1993). During the treatment (contingency management) subjects can earn up to **340** draws from the prize bowl if demonstrating 100% attendance during the 25 weeks of the protocol. Total earnings will vary depending on attendance. With an expected earning of \$2.85 per draw the maximum potential earnings for the CM for 25 weeks is **\$969**. However, actual observed earnings will be significantly less than the potential maximum due to attrition and missed visits.

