The number of individuals with Opioid Use Disorder (OUD) continues to rise with more than 2.5 million affected, along with substantial morbidity and mortality. Several effective medications are available to treat OUD with buprenorphine becoming the primary medication used in the community. Buprenorphine is effective for approximately 50-70% of patients and better results are achieved with the longer duration of treatment. However, the prospect of long-term opioid maintenance is not acceptable to some patients and they eventually request to stop treatment or discontinue it on their own. As many patients who had good treatment response desire to discontinue the medication there is a need to collect evidence about the best strategy to accomplish that. Opioid receptor antagonist naltrexone is approved for relapse prevention following detoxification off opioids. Naltrexone can be started as a first-line treatment following discontinuation off illicit opioids and it may also be used as an adjunct for patients who wish to discontinue buprenorphine maintenance and would like to be protected from relapse. We propose an open-label randomized outpatient trial to evaluate feasibility and efficacy of rapid buprenorphine discontinuation followed by brief course of treatment with long-acting naltrexone (XR-NTX) and to compare it to the standard method of gradual buprenorphine taper.

Individuals with OUD (N=60) who have successfully completed at least 6 months of buprenorphine treatment and do not wish to remain in a long-term buprenorphine maintenance program will be recruited. The first phase includes a 4-week period of stabilization on buprenorphine 2-8 mg at the research clinic to assure that patients are stable, compliant, and free from illicit opioids. Participants that meet the above criteria, approximately 50 individuals, will be randomized 1:1 to: Regimen 1) buprenorphine discontinuation and outpatient transition to XR-NTX with 3 monthly injections, or Regimen 2) buprenorphine discontinuation using a gradual, 5-week long taper. In both groups participants will receive weekly relapse prevention therapy and will be monitored for the duration of the trial, which is 25 weeks post randomization.

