Regimen 1 will include a rapid Monday to Friday oral naltrexone-induction procedure: last dose of BUP on Sat, Sun-Mon 0 mg, Tue 1 mg, Wed 3 mg, Thu 6 mg dose of oral NTX respectively. On Friday, a final 25 mg dose of oral NTX will be given followed by an injection of XR-NTX (Vivitrol; 380 mg IM). All doses of oral NTX will be given in a single or split doses depending on patients' tolerability of the protocol. Throughout the induction adjuvant medications will be administered on standing basis: clonidine 0.1 mg qid, clonazepam 0.5 mg qid, and zolpidem 10 mg HS. Participants will be seen in the clinic daily where they will be monitored for up to 8 hours.

Additional injections of XR-NTX will be administered 4 and 8 weeks after the first injection to participants who provide an opioid-negative urine or pass a naloxone challenge test.

Regimen 2 will include a 5-week BUP taper from the maintenance dose of 8, 6, 4, or 2mg (wk 1: 6, 5, 3 or 2 mg/d, wk 2: 4, 4, 2, or 2 mg/d, wk 3: 3, 3, 2, or 1 mg/d, wk 4: 2 or 1 mg/d, wk 5: 1 mg/d). A buprenorphine/naloxone generic product will be used.

Participants in both regimens will be seen in the clinic for 25 weeks for follow-up after randomization, which will include both the week induction onto Vivitrol in Regimen 1 and the 5 week buprenorphine taper in Regimen 2.

Additional injections of XR-NTX will be offered to patients who continue to express interest in remaining on the medication and are adherent to the time scheduled for the injection (4 weeks after the prior injection). In participants who use opioids and test positive, study physician will determine if it is safe to proceed with the next injection, which may involve administration of naloxone (0.8 mg im).

Outpatient Study Visits and Assessments will occur weekly during the period of BUP maintenance and taper to ensure adherence and to monitor for abstinence. Study visits will take place daily during XR-NTX induction and weekly following injection of XR-NTX or BUP taper in both regimens for the remainder of the study period. Once per week participants will meet with a therapist and complete study assessments. At each

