study visits vitals and a urine toxicology for opioids (morphine, oxycodone, buprenorphine, methadone, propoxyphene, and fentanyl), THC, cocaine, benzodiazepines, amphetamines, and metamphetamines will be collected. They will have scheduled meetings with a study psychiatrist weekly to inquire about medication effects and any changes in their medical/psychological condition following medication discontinuation.

The primary outcome will be the percent of patients successfully transitioned off buprenorphine and abstinent from any opioids at the 25-week trial endpoint. Secondary outcomes will include measures of opioid withdrawal, mood, anxiety and sleep problems, abstinence from other substances, time to relapse or dropout, and adverse effects. We hypothesize that more patients will successfully discontinue buprenorphine in the group that received XR-NTX.

This proposed exploratory trial will be able to inform the design of future research and clinical work. A positive signal that transition from maintenance buprenorphine to XR-NTX is feasible and prevents relapse would encourage a larger trial to replicate and perhaps extend to multiple community based treatment settings. A feasible, well-tolerated, and effective method of helping patients wishing to discontinue treatment with BUP has the potential to expand the population of opioid-dependent individuals benefitting from treatment.

A2. Primary and Secondary Outcome Measures

Primary Outcome: percent of patients successfully transitioned off buprenorphine and abstinent from any opioids at the 25-week trial endpoint.

Secondary Outcomes: 1) Measures of weekly opiate withdrawal (SOWS), mood (Ham-D, BDI), anxiety (HAM-A, STAI), and sleep (MOS-SS) (continuous, longitudinal); 2) Time to relapse (survival outcome); 3) Continuing abstinence at 12 and 25 weeks (dichotomous); 4) Dichotomous weekly summary measure of use (derived by combining urine and self-report, as measured by TLFB) reflecting whether each patient had urine-confirmed opiate-free weeks over the course of treatment and urine-confirmed abstinence from all drugs (dichotomous, longitudinal); 5) Adverse events (SAFTEE) (dichotomous).

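### Does secondary outcome 4 need a written rule so that study-dispensed buprenorphine is not scored as opiate use during the taper?

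*SAP*

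**What the plan says.** SAP A2 lists outcome 4 as a dichotomous, longitudinal summary of use that combines urine with the Timeline Follow-Back (TLFB), "reflecting whether each patient had urine-confirmed opiate-free weeks over the course of treatment and urine-confirmed abstinence from all drugs". SAP C3, Secondary Analyses, models it over time with treatment, time and their interaction. It names no start week and excludes no weeks.

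The SAP's trial description, before A2, specifies "urine toxicology for opioids (morphine, oxycodone, buprenorphine, methadone, propoxyphene, and fentanyl), THC, cocaine, benzodiazepines" and further drug classes at each visit. The Protocol's Urine Toxicology paragraph says the on-site kit "will be used to identify opiates (morphine, oxycodone, buprenorphine, methadone" and closes the list there. Regimen 2 dispenses buprenorphine through week 5, and the SAP counts 25 weeks of follow-up from randomization, "which will include both the week induction onto Vivitrol in Regimen 1 and the 5 week buprenorphine taper in Regimen 2".

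The same SAP description requires participants in the buprenorphine lead-in to be "stable, compliant, and free from illicit opioids", and schedules visits "weekly during the period of BUP maintenance and taper to ensure adherence and to monitor for abstinence". Inclusion criterion 2 likewise asks for three months without illicit opioids in people who are on daily buprenorphine.

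**The concern.** Buprenorphine is an opioid, the panel detects it, and one arm is given it for a fifth of the scored period. Two passages seem to support the strict reading. SAP F3, item 4, warns of withdrawal "if a patient resumes regular opiate, including buprenorphine, use then taking naltrexone", which appears to class buprenorphine as an opiate. The Protocol's incentive scheme awards draws for "every consecutive week of abstinence (all urine samples for a treatment week test negative", with no exception for prescribed drug.

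An analyst who applied that reading would mark every adherent taper participant as not opiate-free in weeks 1-5. Two equally effective regimens would then differ, the taper arm would appear to improve from week 6, and the planned interaction test could report the dosing schedule as a treatment effect. An analyst who exempted dispensed buprenorphine would get a different answer from the same data. The trial is meant to inform a larger one, so the choice could matter later.

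**Working it through.** **Size if scored literally.** The SAP states no figure for outcome 4; its power figure concerns the primary outcome and has no bearing here. Inputs: 25 weeks and a 5-week taper (SAP trial description), and a last Regimen 1 buprenorphine dose on the Saturday before induction, so the XR-NTX week-1 urine may also be positive. Let q be the true weekly opiate-free rate, equal in both arms (assumed).

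- Taper arm: q × (25 − 5)/25 = 0.80q.
- XR-NTX arm: q × 25/25 = q, or q × 24/25 = 0.96q if week 1 is positive.
- False gap: q − 0.80q = 0.20q, or 0.96q − 0.80q = 0.16q.

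| q (assumed) | Gap, XR-NTX week 1 positive | Gap, week 1 negative |
|---|---|---|
| 0.5 | 8.0 points | 10.0 points |
| 0.7 | 11.2 points | 14.0 points |
| 0.9 | 14.4 points | 18.0 points |

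On the Protocol's sparser visits (13 weekly, then 6 twice-monthly, 19 in all), with XR-NTX week 1 positive, the gap is (5 − 1)/19 = 0.21q, or 10.5 points at q = 0.5 and 14.7 at q = 0.7. If only half of taper-week urines read positive, the weekly figures become 2.5/25 = 0.10q and (2.5 − 1)/25 = 0.06q.

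**Effect on the test.** A simulation with no true difference (25 per arm, 25 weeks, logistic GEE with working independence, 300 runs, assumed subject SD 1.5 and mean 1.2 on the logit scale) rejected the interaction in 7.3% of runs with dispensed buprenorphine not counted. With taper weeks 1-5 forced to failure it rejected in 100%, and with XR-NTX week 1 also positive in 99.7%. This model omits the AR(1) term and baseline covariate that C3 specifies. With half of taper urines positive and XR-NTX week 1 positive, a random-intercept logistic model gave 31-51%, and a subject-slope test under serial correlation gave 12-33%. These rates show what literal scoring would do. They are not evidence that it would be used.

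**Which reading the documents support.**

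1. The visit schedule puts adherence and abstinence together during maintenance and taper. If dispensed drug counted as use, every adherent participant would fail and there would be no abstinence to monitor.
2. Lead-in and eligibility define the abstinent state, on buprenorphine, as freedom from illicit opioids.
3. The Protocol's End of Study Form records relapse to opiates and a return to buprenorphine maintenance as separate reasons for ending early.
4. SAP F3, item 6, places relapse after XR-NTX or buprenorphine has been stopped, and the response is an offer of buprenorphine. Taking it is the treatment for relapse.
5. The F3 item 4 warning concerns use that is resumed during naltrexone induction, so it is off schedule. That the author had to add buprenorphine by name suggests the bare word opiate was not assumed to cover it.
6. The incentive rule governs prize draws and defines no endpoint.

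**Whether the data allow the sensible reading.** The Protocol's weekly structured medication count accounts for each dispensed dose, and TLFB is taken at every visit. Scheduled buprenorphine can be told apart from resumed or continued buprenorphine with what is already collected.

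**The case for a change.** The best counter-argument is that the authors write illicit when they mean it and did not do so in outcome 4, while the primary outcome refers to any opioids. In an open-label trial, a scoring choice should not wait for someone who can see the data. Nor is exempting every buprenorphine positive safe: a participant who relapses or withdraws is given clinic buprenorphine, and that should count against successful discontinuation.

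It stands that the text is silent and that a blanket exemption would be wrong. But the line between scheduled and unscheduled buprenorphine follows from the trial's purpose and can be drawn from the medication count and the End of Study Form. A literal scoring would also be hard to miss: when the assay detects the doses, adherent taper participants would show no opiate-free weeks in weeks 1-5, a result fixed by the design before any data. Counting those weeks as not yet off buprenorphine is a coherent measure of a different quantity, and it would only restate the length of the taper.

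The extension to outcomes 2 and 3 does not hold. Saying that all adherent taper participants relapse in week 1 conflicts with how both documents use relapse. A continuing-abstinence rate of 0% in that arm requires counting from randomization, which A2 does not say.

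The all-drug component raises a parallel question, since clonazepam is study-dispensed and benzodiazepines are on the panel; the same reading answers it. Separately, the SAP lists clonazepam for Regimen 1 only and the Protocol for both regimens. That is a consistency matter between the documents, and those passages must be reconciled on their own account.

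**Conclusion.** No change to the plan is needed. The SAP leaves one scoring detail of one secondary outcome unwritten, and the surrounding text leads analysts to fill it sensibly: buprenorphine taken on the assigned schedule is not use, and buprenorphine resumed or continued off schedule is. Under that reading the artefact is removed, apart from any short carry-over after the last dose, which depends on an assay limit the documents do not give.

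Had the literal reading been used, the false gap would be 0.16q to 0.20q on weekly urines, assuming an equal true rate in both arms, a completed taper and an assay that detects the dispensed doses. The interaction rejection rates depend further on assumed variances and on models that are not exactly the planned one. The primary outcome is assessed at week 25, long after the taper, and is unaffected. The SAP's stated purpose, a confidence interval for the odds ratio of treatment success (A4), does not depend on outcome 4.
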